#### Stop dates

Sponsor:	TauRx Therapeutics Ltd.		
Protocol:	TRx-237-039		
Document Version No.:	3.0	Document Date:	07-JUN-2023

---

- For missing stop day only: Day will be imputed as the last day of the month (i.e., 28, 29, 30, or 31) or the last day of study contact if earlier.
- For missing stop day and month: Day and month will be imputed as the last day of the year (i.e., 31 December) or the last day of study contact if earlier.

#### **4.3. Computing Environment**

Statistical analyses will be performed using SAS® statistical software (Version 9.4 or higher), unless otherwise noted. Medical History and AEs will be coded using Medical Dictionary for Regulatory Activities (MedDRA) version 20.1. Recently used medications and concomitant medications will be coded using the World Health Organization (WHO) Drug version from 01MAR2017.

In addition, main occupation during working life is to be provided, which will be coded using the Standard Occupational Classification, 2010, Volume 2 The Coding Index, UK Office for National Statistics.

More coding details are described in the Data Management Plan.

#### **4.4. Withdrawals, Dropouts, Loss to Follow-up**

Subjects who withdraw from the study were not to be replaced.

For subjects who cease taking study drug but who wish to continue in the study, the planned schedule of assessments should be followed, except for the collection of blood samples for MT concentrations (with protocol version 7.0 and 7.0 UK). These subjects will be classified as “the off-treatment-on-study” (TOTOS) group. A subgroup of TOTOS are the subjects with antidementia therapy initiation (AchEI and/or memantine) after informed consent.

Interruption of dosing for up to a maximum of 14 consecutive days may be allowed if the Investigator determines this is indicated (e.g., due to an AE or any other reported change in the subject’s physical condition in the judgment of the Investigator) on a maximum of two occasions. If this is exceeded, study drug would need to be discontinued; however, the subject will be encouraged to continue study participation off-treatment (TOTOS). If subjects stopped the dosing without the Investigator’s approval, they could get back on treatment.

For each subject who withdraws from the study, the decision will be made as part of the BDRM if the withdrawal is potentially treatment-related. For potentially treatment-related dropouts, the fraction of subjects who withdrew at a given time point will be calculated for each treatment group. In addition, a table and figure of the Kaplan-Meier estimator of time to potential treatment-related withdrawal will be given.

Sponsor:	TauRx Therapeutics Ltd.		
Protocol:	TRx-237-039		
Document Version No.:	3.0	Document Date:	07-JUN-2023

---

A separate listing of the subjects with antidementia therapy initiation will be provided, including the reason if available. Furthermore, listings will be provided for the efficacy endpoints showing all assessments and assessments which are impacted by antidementia therapy initiation being flagged.

#### 4.5. Missing, Unused, and Spurious Data

In the estimand approach multiple imputation will be applied in hypothetical strategies (see Section 5.9.1). In the MITT analysis multiple imputed data are included as a sensitivity analysis.

##### 4.5.1. Upscaling

Upscaling will be applied in the presence of missing and/or non-valid data, as long as there are sufficient data available.

According to Section 2.5 efficacy scales may have been performed remotely. Based on the document *TRx-237-039: Impact of Remote Administration of Efficacy Scales* the following items are not possible to assess remotely:

- ADAS-cog13: All but Orientation. All others, except Ideational Praxis, Number Cancellation, and Commands (sub-subdomains 3 and 4), are possible, when assessment is done by video call. For ADAS-cog11 without Ideational Praxis and Commands the maximal achievable total score is 60.
- MMSE: Naming, Comprehension, Reading, Writing, Drawing (may possible, when assessment is done by video call).

For ADSC-ADL23 the following items are affected by COVID-19 restrictions:

- Travel, Shopping, Keeping appointments, Left alone, Talk about current events, and Pastime (hobby or game). The maximal achievable total score of the remaining items is 58.

When these items are excluded in the COVID-19 sensitivity analysis, the remaining items will be upscaled as described.

For the end of treatment value (see Section 5.9.1.3), the last available upscaled on-treatment value will be used for analysis.

##### 4.5.1.1. ADAS-cog11 and ADAS-cog13

The ADAS-cog11 / ADAS-cog13 total score is the sum of four / five domain scores (see Appendix 12.2.1).

The Word Recall subscore will be calculated as the mean of the non-missing scores from the three trials, rounded to 2 decimal places. The other subscores are obtained directly from the CRF page.

Within a given domain, there may be some missing subscores. If the sum of the maximum possible score of the non-missing items  $m$  is greater or equal to one half (50%) of the maximum possible score

Sponsor:	TauRx Therapeutics Ltd.		
Protocol:	TRx-237-039		
Document Version No.:	3.0	Document Date:	07-JUN-2023

for the domain  $t$ , the domain score will be scaled up using the formula:  $t*s/m$ , with  $s$  being the score of the non-missing subscores.

Otherwise, the domain score will be missing. If any domain score is missing, the ADAS-cog11 / ADAS-cog13 total score will be missing.

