  - In the remote administration of the ADAS-cog13 (if applicable at that visit), the standard (*i.e.*, validated) mode of administration has been adapted to enable data to be captured by videoconference, with the exception of Commands (only partially supported, and thus a total score cannot be calculated for this subset), Ideational Praxis, and Number Cancellation. Due to these missing data (not all subtests can be administered remotely), total scores will not be calculated directly for the remote administration of the ADAS-cog13 but a derived upscaled score will be used for analysis as defined in the SAP.
- The MMSE, CDR, and ADCS-ADL23 may be performed either in the clinic at the site or, if deemed necessary to protect subjects due to COVID-19, in the subject's home or at other safe, suitable alternatives in person or remotely by speakerphone. If assessments are performed remotely, the rater will confirm the identity of the subject and study partner before proceeding. The approved site raters will document the assessment as they would if performing the assessment in person; source data and audio recordings will still be captured via the Virgil system.
  - In the remote administration of the MMSE (if applicable at that visit), the approved site rater will administer as much of the MMSE as possible. For those elements that cannot be administered remotely, the rater will confirm that these were omitted before submitting the data to MedAvante-ProPhase per usual practice. Due to missing data, total MMSE scores for remote assessments will not be directly calculated but upscaled as per the SAP.
  - In the remote administration of an ADCS-ADL23 or CDR (if applicable at that visit), all items will be scored.
- All MRI scans are to be performed at approved MRI centers using approved scanners; no alternative scanners will be accepted and there is to be no change in scanner for a given subject over the course of the study.
  - Guidance will be provided for scheduled MRI visits at approved imaging centers that may be closed due to COVID-19, including acceptable windows outside the scheduled visit window during which MRI scans can still be performed at approved imaging centers and would be accepted for analysis.

---

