## 2.9. Efficacy, Pharmacokinetic, Safety, and Other Variables

### 2.9.1. Efficacy Variables

#### 2.9.1.1. Primary Efficacy Variables

Primary efficacy variables are (assessed at Baseline, 13, 26, 39, 52, 78, and 104 weeks, or early termination):

- ADAS-cog11
- ADCS-ADL23

The **ADAS-cog11** is the cognitive subscale of the ADAS, originally proposed with 11 items (domains: memory, praxis, orientation, and language), resulting in scores that range from 0 to 70, with higher numbers indicating greater impairment. For the ADAS-cog13 two additional items have been added (in domain Memory: Delayed Word Recall, and as a new domain Attention: Number Cancellation) to provide additional sensitivity to change in cognition at earlier stages of the disease, resulting in a maximal score of 85 (see Appendix 12.2). As the original ADAS-cog11 was used in the earlier Phase 3 studies (TRx-237-005, TRx-237-015), that score will be derived from the assessment of the ADAS-cog13 for the primary analyses. ADAS-cog13 will be analyzed as an explorative efficacy variable.

The **ADCS-ADL23** includes 23 items describing the performance of activities of daily living (ADL) by AD subjects with scores ranging from 0 to 78 and higher numbers indicating lesser impairment.

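### The SAP scoring rule sets every video-administered ADAS-cog13 total to missing, although 70 of 85 points are observable and the protocol says an upscaled score will be used

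*SAP*

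**What the plan says.** **Scoring rule.** In SAP 4.5.1.1 the ADAS-cog11 / ADAS-cog13 "total score is the sum of four / five domain scores (see Appendix 12.2.1"). A domain with missing items is upscaled when the maximum of its non-missing items "is greater or equal to one half (50%) of the maximum possible score" for that domain. If it falls short, that domain is missing, and the rule continues: "If any domain score is missing, the ADAS-cog" total is missing too.

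**Domain content.** SAP 2.9.1.1 says that ADAS-cog13 adds Delayed Word Recall to Memory and, "as a new domain Attention: Number Cancellation". The table in SAP 12.2.1 lists no other Attention item and gives this one a maximum of 5.

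**Remote limits.** SAP 4.5.1 says that without video only Orientation can be assessed. It continues: "All others, except Ideational Praxis, Number Cancellation, and Commands (sub-subdomains 3 and 4), are possible, when assessment is done by video call". Protocol 10.2.1 names the same three items.

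**Commitment to upscale.** Protocol 10.2.1 says that a remote ADAS-cog13 total will not be calculated directly, "but a derived upscaled score will be used for analysis as defined in the SAP". SAP 12.1.1, responding to the FDA COVID-19 guidance, likewise records items that cannot be given remotely as missing and relies on upscaling for them.

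**Use of the scale.** ADAS-cog13 is exploratory. It has a double-blind MMRM with an MMSE 20-27 subgroup (SAP 5.10.1). It also appears in post hoc open-label summaries, line graphs and t-tests (SAP 6.12) and in Week 52 biomarker correlations (SAP 7.3.3).

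**The concern.** The rule works while every domain keeps some items that can be given remotely. Attention has one item, and that item cannot be given by video, so the domain can never reach 50%. The any-domain condition then discards the whole total. The documents announce upscaling for exactly this situation, but the rule they point to returns nothing.

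At stake are ADAS-cog13 totals at visits that the SAP allows to be remote. Repeated-measures estimates at those visits rest on fewer subjects, and the t-tests, which use observed change, drop the subject at that visit. A programmer must either discard data that the protocol says will be used or invent a derivation that is not documented.

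**Working it through.** **Inputs.** Item maxima and domains come from SAP 12.2.1, items not available by video from SAP 4.5.1 and protocol 10.2.1, and the domain rule from SAP 4.5.1.1. With t the domain maximum, m the maximum of the available items and s the observed score, the domain score is t × s / m if m / t ≥ 0.5 and missing otherwise.

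**Check of the plan's own figures.** ADAS-cog11 items: Memory 10 + 12 + 5 = 27, Praxis 10, Orientation 8, Language 25; total 70. Without Ideational Praxis and Commands, 70 − 5 − 5 = 60, as SAP 4.5.1 states. Adding Delayed Word Recall (10) and Number Cancellation (5) gives 85, as SAP 2.9.1.1 states.

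**Video visit, available / maximum by domain:**

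| Domain | ADAS-cog11 | ADAS-cog13 |
|---|---|---|
| Memory | 27/27 | 37/37 |
| Attention | not in scale | 0/5 = 0%, missing |
| Praxis | 5/10 = 50%, passes | 5/10 = 50%, passes |
| Orientation | 8/8 | 8/8 |
| Language | 20/25 = 80% | 20/25 = 80% |
| Points available | 60/70 = 86% | 70/85 = 82% |
| Total | computed | missing |

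Attention is the only failing domain. Commands is partly supported by video. Counting it in full gives Language 25/25 and 75/85 = 88%, and the ADAS-cog13 total is still missing.

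**Telephone only.** Orientation alone is available: 8/85 = 9% for ADAS-cog13 and 8/70 = 11% for ADAS-cog11. Memory, Praxis and Language fail, so both totals are missing.

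**A total-level rule.** SAP 4.5.1.2 and 4.5.1.3 upscale ADCS-ADL23, MMSE and CDR-SOB when at least two thirds of the total maximum is available. A video ADAS-cog13 would qualify (0.82 > 0.67) and be scored 85 × s / 70, a factor of 1.214. Telephone (0.09) would not qualify.

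**Visits exposed.** SAP 2.5 requires Baseline, Week 52 and early-termination assessments on site. That leaves Weeks 13, 26 and 39 in the double-blind MMRM. In the post hoc outputs, the summaries cover Weeks 78 and 104, the t-tests also use Week 26, and the Baseline-to-Week 104 version of the graphs carries the double-blind visits.

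**The case against.** **The protocol delegates the rule.** Protocol 10.2.1 leaves the definition to the SAP, protocol 17.4.5 makes upscaling of partial data permissive, and SAP 4.5.1 makes it depend on sufficient data. On this view no promise is broken. That softens the conflict but does not remove it: protocol 10.2.1 names ADAS-cog13 and says an upscaled score will be used, SAP 12.1.1 repeats the intention, and no exception for Attention was found.

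**A domain rule is defensible.** It avoids inferring a wholly unobserved domain from others. This stands as a real cost of the total-level rule, which would also weight the shared items differently from ADAS-cog11.

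**The consequences are small.** Much of this stands. A reader might infer that the Week 52 treatment contrast or the biomarker correlations are damaged. The documents do not support that: both use Baseline and Week 52, which the SAP requires on site, and SAP 3.2 lists a remote assessment at either visit as a protocol deviation. Protocol 10.2.1 is looser about Visit 7, so the protection holds only if the SAP requirement was followed.

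A reader might also infer that all data from a video visit are lost. Only the 13-item total is lost. The same session still gives an ADAS-cog11 total, and the COVID-19 Composite Scale keeps Delayed Word Recall and omits Number Cancellation.

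**Remote use may have been rare.** Remote scales needed advance Sponsor approval case by case, and no count is given. This stands.

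**Conclusion.** The concern holds for video administration of ADAS-cog13. Under the rule as written, 100% of video-administered totals are missing because one 5-point item cannot be given, with 70 of 85 points observable. This is a stated rule that contradicts a stated commitment, so it is wrong as written and not merely short of detail.

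The reach is limited. ADAS-cog13 is exploratory, and this defect touches no primary or secondary endpoint. The loss falls on the intermediate double-blind visits and on Weeks 26, 78 and 104 in post hoc outputs. In-person home visits are not remote administration and are unaffected. Telephone-only totals stay missing under either the current or the two-thirds rule, for ADAS-cog11 too, and are not part of this point.

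The conclusion rests on reading SAP 4.5.1.1 and 12.2.1 literally, and on Baseline and Week 52 having been on site. The number of video visits is not stated, so the loss can be given as a proportion of those visits but not as a count. Nor do the documents show whether the loss differs by arm or severity. Protocol 10.2.3 expects COVID-19 to affect certain MMSE groups, but that does not establish bias here.

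**What to change.** For ADAS-cog13, replace the any-domain condition with the total-score rule that the SAP already uses for three other scales: upscale when at least two thirds of the 85 points are available, giving 85 × s / 70 for a video visit. Show the results under the current rule as a sensitivity analysis, and report the number of video-administered ADAS-cog13 assessments by visit and arm.

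The cost is one scoring sentence, one derivation and a rerun of the ADAS-cog13 outputs. The change must be labelled as made after the April 2022 data snapshot and partial unblinding recorded in SAP section 10, so it is post hoc for the double-blind phase. Its statistical downside is that the unobserved Attention item is inferred from the other domains.

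If that inference is not acceptable, state in SAP 4.5.1.1 that no remote ADAS-cog13 total is analysed, and bring protocol 10.2.1 and SAP 12.1.1 into line. That costs only wording and leaves the analysis unchanged, but gives up the video totals.

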#### 4.5.1.2. ADCS-ADL23

For ADCS-ADL23, it is possible to answer items with “Don’t Know”. If not more than four items are answered that way, the items are not missing and will count as 0. Upscaling of the other missing values is then done as follows:

Let  $m$  be the maximal obtainable score of the non-missing items (including “Don’t Know”), and  $s$  the score of the non-missing items (including “Don’t Know”). If  $m/78 < 2/3$ , then the total score is set to missing, otherwise upscaling will be performed using the formula:  $78*s/m$ .

In case of more than four items answered with “Don’t Know”, the Total score is not provided by the data vendor. Therefore, a more complex upscaling algorithm will be applied to calculate the Total score. Since it cannot be decided, which four “Don’t Know” items will count as 0 and which not, the mean of the maximal obtainable scores of the items answered with “Don’t Know” is used in the following upscaling rule:

Let  $x$  be the mean of the maximal obtainable scores of the items answered with “Don’t Know”,  $m_2$  the maximal obtainable score of the non-missing items (excluding “Don’t Know”) plus  $4*x$ , and  $s$  the score of the non-missing items (excluding “Don’t Know”) (plus  $4*0$ ).

If  $m_2/78 < 2/3$ , then the total score is set to missing, otherwise upscaling will be performed using the formula:  $78*s/m_2$ .

#### 4.5.1.3. MMSE, CDR-SOB

The following rule is true for MMSE, and CDR-SOB.

Let  $t$  be the maximal score (MMSE: 30, CDR-SOB: 18),  $m$  the maximal obtainable score of the non-missing items, and  $s$  the score of the non-missing items. If  $m/t < 2/3$ , then the total score is set to missing, otherwise upscaling will be performed using the formula:  $t*s/m$ .

#### 4.5.1.4. Composite Scale and COVID-19 Composite Scale

For the two composite scales, upscaling will be performed analogously to the algorithm as described above (see Sections 4.5.1.1 and 4.5.1.2), restricted to the respective composite scale subscores/ items. If one of the two scales is missing, the respective composite scale missing.

#### 4.5.2. Multiple Imputation

Upscaling will be performed prior to the use of multiple imputation.

Sponsor:	TauRx Therapeutics Ltd.		
Protocol:	TRx-237-039		
Document Version No.:	3.0	Document Date:	07-JUN-2023

Multiple imputation will be performed only for the double-blind treatment phase data of the two co-primary endpoints and the secondary endpoint MRI whole brain volume.

Missing values will be imputed multiple times to account for the uncertainty about the true values to impute. A multivariate imputation by fully conditional specification (FCS) methods will be used, which handles arbitrary missing patterns. This will be applied using the FCS statement in the MI procedure in SAS®.

The imputation model uses the same fixed factors and covariates as in the respective analysis models, unless specified otherwise.

The seed of **237039** was pre-specified in the study protocol and must be used in the final run. A total of 50 imputed datasets will be generated.

For the MITT populations data after multiple imputation are analyzed in a sensitivity analysis. The imputation model will not include the treatment indicator.

Sample SAS code (will be fully validated at the analysis stage):

```
PROC MI DATA=dataset SEED=237039 NIMPUTE=50 OUT=datami;  
  CLASS visit severity region prioruse;  
  FCS REG(adascog11 = visit severity region prioruse adascog11bl);  
  FCS REG(adcsadl23 = visit severity region prioruse adcsadl23bl);  
  FCS REG(mriwbv = visit severity region prioruse mriwbvbl);  
  VAR visit severity region prioruse adascog11bl adcsadl23bl mriwbvbl adascog11 adcsadl23  
       mriwbv;  
  RUN;
```

Imputed values will not be edited to fit their respective definition area, since they are not equivalent to observed data and serve only to help estimating covariances between variables.

In sensitivity analyses of the primary estimand (see Section 5.9.1.1) the following two strategies will be followed, as summarized in Section 4.5.2.1 and 4.5.2.2:

#### **4.5.2.1. Imputing missing data for both treatment groups based on data seen in control group**

Outcomes are imputed for all treatment groups as if they would have continued on the control, which assumes the statistical behavior of control- and HMTM-treated subjects is the statistical behavior of control-treated subjects.

Sponsor:	TauRx Therapeutics Ltd.		
Protocol:	TRx-237-039		
Document Version No.:	3.0	Document Date:	07-JUN-2023

This will be implemented by the MNAR statement, which imputes missing values by using the pattern-mixture model approach:

Sample SAS code (will be fully validated at the analysis stage):

```

PROC MI DATA=dataset SEED=237039 NIMPUTE=50 OUT=datami;
  CLASS visit severity region prioruse;
  FCS REG(adascog11 = visit severity region prioruse adascog11bl);
  FCS REG(adcsadl23 = visit severity region prioruse adcsadl23bl);
  FCS REG(mriwbv = visit severity region prioruse mriwbvbl);
  MNAR MODEL (adascog11 / MODELOBS=(treatment='control'));
  MNAR MODEL (adcsadl23 / MODELOBS=(treatment='control'));
  MNAR MODEL (mriwbv / MODELOBS=(treatment='control'));
  VAR visit severity region prioruse adascog11bl adcsadl23bl mriwbvbl adascog11 adcsadl23
mriwbv;
  RUN;

```

#### 4.5.2.2. Imputing missing data for each treatment group based on data seen in their own group

Outcomes are imputed assuming that subjects would follow their initial treatment (rather than switching to control after discontinuation), conditional on baseline and pre-withdrawal data included in the analysis. Therefore, the treatment arm will be included in the imputation model.

Sample SAS code (will be fully validated at the analysis stage):

```

PROC MI DATA=dataset SEED=237039 NIMPUTE=50 OUT=datami;
  CLASS visit severity region prioruse treatment;
  FCS REG(adascog11 = visit severity region prioruse adascog11bl treatment);
  FCS REG(adcsadl23 = visit severity region prioruse adcsadl23bl treatment);
  FCS REG(mriwbv = visit severity region prioruse mriwbvbl treatment);
  VAR visit severity region prioruse treatment adascog11bl adcsadl23bl mriwbvbl adascog11
adcsadl23 mriwbv;
  RUN;

```

Sponsor:	TauRx Therapeutics Ltd.		
Protocol:	TRx-237-039		
Document Version No.:	3.0	Document Date:	07-JUN-2023

#### 4.5.2.3. Analysis of multiple imputed data

Each of the 50 imputed datasets will be analyzed as done for the non-multiple imputed data, by adding the BY \_IMPUTATION\_ statement. Afterwards, these 50 results will be combined using standard Rubin's combination rules. Since the analyses results are assumed to be normally distributed no additional transformation will be necessary.

```
PROC MIANALYZE PARMs (CLASSVAR=FULL) = mxparms;
  CLASS treatment visit severity region prioruse;
  MODELEFFECTS treatment/visit severity region prioruse scorebl;
  BY parameter;
  ODS OUTPUT PARAMETERESTIMATES=mimxparms;
  RUN;
```

